3. INVESTIGATIONAL PLAN

3.1. Study design and methodology

This phase 2/3 study will evaluate the efficacy and safety of ABX464 50mg QD (oral capsule), on treating inflammation and preventing acute respiratory failure in patients infected with SARS-CoV-2.

Eligible patients will be randomized according to a 2:1 ratio into 2 treatment cohorts as follows:

- Standard of Care + ABX464 50mg QD: 533 patients
- Standard of Care + Placebo cohort: 267 patients

[figure not shown]
Upon randomization, patients will be stratified according to:

- Age \geq 65 years or $<$ 65 years (with at least one risk factor)
- Inpatient or outpatient, at the time of enrolment

Study design:

The study will consist of 3 periods:

- Treatment phase: randomized patients will be treated for 28 days
- Safety follow-up phase of 21 days
- Exploratory follow-up of the pulmonary function 3 months after the last study drug intake.

* Considering sites potential organization and the quarantine requirements in participating countries, randomization visit can be splitted into 2 separated visits. However, the interval between these 2 visits cannot exceed 48 hours to ensure patients start the study treatment at an early stage of the disease.

From Day 0 onwards, randomized patients will be followed by the investigational site at 7 days (D7 +/- 2 days), 14 days (D14 +/- 2 days), 21 days (D21 +/- 2 days) and finally 28 days (D28 +/- 2 days) after randomization.

Should a patient be hospitalized at D0, Day 7 visit will be an on-site visit.

Should a patient not be hospitalized, considering a quarantine period might be applied for infected patients, a remote medical monitoring will be performed by the investigator or his designee every 2 days from D0 and until D14. Every attempt to perform the Day 7 on-site visit should be made anyway. For outpatients, an oximeter will be provided at Day 0. During the remote medical monitoring, the patient will be asked to self-measure every day the oxygen saturation, body temperature and will be asked for any potential signs of COVID-19 infection worsening. Subsequent, D14, D21 and D28 will be on-site visits.

If no quarantine period is applied or if patients migration to the study site is acceptable as per local regulation, outpatients will perform a D7 visit on-site, and the same examinations as hospitalized patients will be performed.

At randomization visit, all patients must have been diagnosed for SARS-CoV-2 infection by PCR or Rapid Antigen tests either performed on site or in a private laboratory prior to the visit. The time between PCR or Rapid Antigen tests diagnosis and first study drug intake should not exceed 48 hours. A long-term follow-up is scheduled as an onsite visit for patients having been hospitalized during the course of the study. This follow-up will be performed 3 months after the last study drug intake and will consist of a respiratory function exploration. In addition, investigators

will report the disease severity rating using a 7-point ordinal scale.

3.2. Dose limiting toxicity (DLT)

A dose limiting toxicity (DLT) is defined as a grade 3 or higher adverse event as defined by the Common Terminology Criteria for Adverse Events (CTC-AE V5.0) considered by the study Data and Safety Monitoring Board (DSMB) as probably or definitely related to study treatment.

Every grade 3 or higher adverse event will be immediately (within 24 hours) reported to the DSMB for causality assessment.

In case of a life threatening (grade 4) adverse reaction probably or definitely related to study treatment, all safety data will be reviewed by DSMB members within 7 days of first notification of the event by the investigating site.

In that case, new enrolment and treatment of ongoing patients will be discontinued and will re-start upon DSMB recommendation and after regulatory approvals are obtained.

3.3. Data and Safety Monitoring Board

An independent Data and Safety Monitoring Board (DSMB), with expertise and experience in virology, immunology, and biostatistics, and without direct involvement in the conduct of the trial, will be set up specifically to guarantee effective protection of patients, ensure the ethical conduct of the trial, benefit/risk ratio of the trial, and to ensure the independent review of the scientific results during the trial and at the end of the trial.

The DSMB will meet first after the 20 first patients are enrolled and treated for at least 4 weeks (D28) and then every month after this first meeting.

The DSMB will oversee the adequate balance of baseline characteristics (i.e. gender, disease duration, previous and concomitant CD medication) among the treatment groups and will review safety and efficacy data.

Furthermore, all potential causally-related Serious Adverse Events within 7 days of the initial notification by an investigating site. Every grade 3 or higher adverse event will be reported within 24 hours to the DSMB for causality assessment.

The DSMB has a consultative role. It will inform the Sponsor who will decide whether the DSMB recommendation will be followed. Besides, the DSMB may recommend the early termination of the trial at any time if an unacceptable toxicity occurs.

A DSMB charter must be available upon submission of the trial (initial protocol) to the respective competent authorities.

3.4. Steering Committee

A study steering committee will oversight the practical aspects of the study especially with regards to the evolving nature of the COVID-19 infection.

The Steering Committee will work in conjunction with the DSMB. Specific responsibilities of the Steering Committee include, but are not limited to, the following: ensure the overall supervision of the MiR-Age study, take actions to reduce deviations from the protocol to a minimum, review of the progress of the study, make any recommendations for modifications to the protocol that might be medically or ethically relevant during the course of the study.

The Steering Committee will be able to terminate the trial if the medical relevance of the MiR-Age is substantially modified during its execution. ABIVAX and principal investigator will agree, in writing prior to the start of the study, to the charter of the Steering Committee.

3.5. Duration of study participation

There is no screening visit in the present protocol.

After the collection of the signed informed consent, patients will be treated for 28 days, then will go through a 21-days safety follow-up period.

Finally, an exploration of the pulmonary function will take place 3 months after the last treatment dose intake for patients with at least 1 hospitalization during the study. For outpatients, a remote contact will be performed 3 months after the last treatment dose intake to collect their survival status.

Therefore, the total study duration for a given participant is up to 4 months.

4. STUDY POPULATION

4.1. Number of Patients/Centers

Approximately 800 patients will take part in this study with a maximum number of patients of 1034 following the interim analysis. These patients will be enrolled in approximately 75 sites located in Europe and Latin America (i.e. France, Germany, Belgium, Italy, Spain, United Kingdom, Brazil, Mexico, Chile, Peru).

4.2. Eligibility Criteria

4.2.1. Inclusion Criteria

A patient will be eligible to participate in this study if ALL the following criteria are met:

1. Adult (≥ 18 years old) men or women, hospitalized or not hospitalized, diagnosed for SARS-CoV-2 infection by PCR or Rapid Antigen tests (approximately 48 hours prior to randomization), with at least one associated risk factor. Considered risk factors are:
 - Age ≥ 65 years
 - Obesity defined as BMI ≥ 30
 - Recent history of uncontrolled High Blood Pressure
 - Treated diabetes (type I or II)
 - History of ischemic cardiovascular disease
2. Symptomatic patients must present at least 1 of the following symptoms at enrollment: fever or perceived fever for more than 24 hours, headache, sore throat, dry cough, fatigue, chest pain or choking sensation (with no associated respiratory distress), myalgia, anosmia, ageusia, or gastro-intestinal symptoms.
3. Patients with pulse oximetry arterial saturation (SpO₂) $\geq 92\%$ on room air at enrolment.
4. Patients with the following hematological and biochemical laboratory parameters obtained within 7 days prior to D0:
 - Hemoglobin > 9.0 g dL⁻¹
 - Absolute Neutrophil Count ≥ 1000 mm⁻³;
 - Platelets $\geq 100,000$ mm⁻³;
 - Creatinine clearance ≥ 50 mL min⁻¹ by the Cockcroft-Gault formula
 - Total serum bilirubin $< 2 \times$ ULN
 - Alkaline phosphatase $< 2 \times$ ULN, AST (SGOT) and ALT (SGPT) $< 3 \times$ ULN;
5. Women of childbearing potential and men receiving the study treatment and their partners must agree to use a highly effective contraceptive method during the study and for 6 months (180 days) after end of study or early termination. Contraception should be in place at least 2 weeks prior to enrolment. Women must be surgically sterile or if of childbearing potential must use a highly effective contraceptive method. Women of childbearing potential (WOCBP) will enter the study after confirmed menstrual period and a negative pregnancy test. Highly effective methods of contraception include true abstinence, intrauterine device (IUD) or hormonal contraception aiming at inhibition of ovulation, intrauterine hormone releasing system, bilateral tubal ligation, vasectomized partner. True abstinence is defined when this is in line with the preferred and usual lifestyle of the patient. In each case of delayed menstrual period (over one month between menstruations) confirmation of absence of pregnancy is required. This recommendation also applies to WOCBP with infrequent or irregular menstrual cycle. Female and male patients must not be planning pregnancy during the trial and for 6 months post completion of their participation in the trial. In addition, male patients should use condom during the trial and for 6 months (180 days) post completion of their participation in the study. Male patients must not donate sperm as long as contraception is required. *For the purpose of this protocol, a woman is considered of childbearing potential (WOCBP), i.e. fertile, following menarche and until becoming post-menopausal unless permanently sterile. Permanent sterilisation methods include hysterectomy, bilateral salpingectomy and bilateral oophorectomy. A postmenopausal state is defined as no menses for 12 months without an alternative medical cause. A high follicle stimulating hormone (FSH) level in the postmenopausal range may be used to confirm a*

post-menopausal state in women not using hormonal contraception or hormonal replacement therapy. However, in the absence of 12 months of amenorrhea, a single FSH measurement is insufficient. Finally, a man is considered fertile after puberty unless permanently sterile by bilateral orchidectomy.

6. Patients must understand, sign and date the written voluntary informed consent form at the visit prior to any protocol-specific procedures.
7. Patients able and willing to comply with study visits and procedures as per protocol.
8. Patients should be affiliated to a social security regimen (for French sites only).

4.2.2.Exclusion Criteria

Patients who meet any of the following exclusion criteria will be excluded from the study:

1. Patients with moderate or severe acute respiratory failure or requiring non-invasive ventilation or oxygen or with SpO₂ < 92% or tachypnea (respiratory rate ≥ 30 breaths/min).
2. Patients treated with immunosuppressors and/or immunomodulators (cf. Appendix #2).
3. Engrafted patients (organ and/or hematopoietic stem cells).
4. Patients with uncontrolled auto-immune disease.
5. Patients with known or suspected active (i.e. not controlled) bacterial, viral (excluding COVID-19) or fungal infections.
6. Patients with preexisting, severe and not controlled organ failure.
7. History or active malignancy requiring chemotherapy or radiation therapy (excluding 2 years disease free survivor patients).
8. Pregnant or breast-feeding women.
9. Illicit drug or alcohol abuse or dependence that may compromise the patient's safety or adherence to the study protocol.
10. Use of any investigational or non-registered product within 3 months or within 5 half-lives preceding baseline, whichever is longer.
11. Hypersensitivity to ABX464 and/or its excipients.
12. Any condition, which in the opinion of the investigator, could compromise the patient's safety or adherence to the study protocol.

5. STUDY ASSESSMENTS AND PROCEDURES

5.1. Study Flow Chart

A detailed study flow chart (with all assessments) is displayed hereafter.

	TREATMENT PERIOD						UN SCH. VISIT	FOLLOW-UP PERIOD							
	V1 ¹³	Remote Medical Monitoring of Outpatients to be done every 2 days between D0 and D14	V2	V3	V4	V5 - End of treatment		V6 - Safety follow-up	V7 – long-term Fup						
	D0		D7 for hosp. Patients/and potentially outpatients	D14	D21	D28		D48	3 months post last SD intake						
GENERAL															
Signed inform consent form collection	X														
Check of IN/EX Criteria	X														
Demographic data collection	X														
Medical History	X														
Current medications	X	X	X	X	X	X	X	X							
7-point Ordinal scale	X		X	X	X	X		X	X						
PHYSICAL EXAMS															
Physical Examination (including vital signs) ¹	X		X	X	X	X	X	X							
Oxymeter and patient diary dispensation/collection	X			X											
Remote monitoring of body temperature, SPO2 and Clinical Signs of COVID-19		Monitoring every 2 days between D2 and D14													
Outpatients mortality status ¹²									X (remote)						
Body Weight (kg) & Height (cm) measurements ²	X														
ECG ³	X		X	X	X	X	X	X							
ANALYSIS TO BE PERFORMED LOCALLY															
Blood Pregnancy test (WOCBP) ⁴	X							X							
Hematology + Biochemistry ⁵	X		X	X	X	X	X	X	X ¹⁰ (Hb only)						
BIOBANKING															
Plasma (CRP, Troponin I & T, D-Dimer ⁶)	X		X	X	X	X	X								
Immunophenotyping and cells activation markers ⁷	X			X		X	X								
Blood sample Cytokines ⁸	X			X		X	X								
Nasopharyngeal and blood samples for viral load assessment	X		X	X	X	X	X								
Samples for miRNA-124 (Blood PAXgene tube)	X		X			X									
Haemostasis function exploration	X		X	X	X	X	X								
IMAGING															
Chest CT-SCANS ⁹	(X)		For hospitalized patients only – to be performed at discharge												
RESPIRATORY FUNCTION EVALUATION¹⁰															
Medical Research Council Dyspnea scale	For hospitalized patients only – to be performed at discharge								X						
Spirometry	(For hospitalized patients only – to be performed at discharge)								(X)						
CMDC	(For hospitalized patients only – to be performed at discharge)								(X)						
TREATMENT ALLOCATION															
Randomization	X														
ABX464/placebo treatment dispensation ¹¹	X														
ABX464/placebo treatment accountability						X									
SAFETY															
Adverse Events recording	X	X	X	X	X	X	X	X							

¹ **Physical examinations:** a complete physical examination will be performed at D0, at the End of treatment visit (EoT), and at D48. Only differences from baseline will be reported at every other visit

² **Body Weight and Height:** Body weight and height will be measured at D0 for BMI assessment.

³ **ECG:** A 12-Leads ECG will be performed at every on-site study visit.

⁴ **Blood pregnancy test:** Applicable to all women of childbearing potential at D0 and at D48. In order not to limit the patient enrollment a urine pregnancy test can be performed in addition if the blood test result is not available at the time of randomization.

⁵ **Hematology + Biochemistry:** samples to be taken at every on-site study visit (except D7 for outpatients if not possible) and analyzed locally.

⁶ **CRP, Troponin I & T and D-Dimer:** samples to be taken at every on-site study visit (except D7 for outpatients if not possible) and sent to central laboratory for biobanking purpose.

⁷ **Immunophenotyping and cells activation markers:** samples will be taken in selected sites and for approximately 100 patients.

⁸ **Blood sample Cytokines:** samples will be taken in all sites for all patients.

⁹ **Chest CT-scan:** procedure concerns hospitalized patients only (whenever the hospitalization occurs during the course of the study). Images taken at discharge (\pm 7 days) will be assessed locally, then collected and sent to a blinded central reader for descriptive analysis of the lesions. If available at D0, Baseline CT scans of hospitalized patients will be sent to Central Reader for comparison purpose.

¹⁰ **Respiratory function evaluation:** This evaluation will be performed only in patients who were hospitalized during the course of the study. For these patients the MRC Dyspnea assessment scale must be used at discharge and 3 months after last study drug intake. For sites having adequate facilities a PFT (FEV₁ and slow and forced Vital Capacity) and a Carbon Monoxide Diffusing Capacity (CMDC) evaluation will be performed at discharge and 3 months after last study drug intake (optional assessments). For this last test, a blood sample for hemoglobin assessment must be taken within 48hrs prior to the CMDC test.

¹¹ **ABX464/placebo treatment dispensation:** treatment dispensation will be allowed once all the selection criteria are confirmed, including laboratory assessments for patients' eligibility confirmation.

¹² **Outpatients mortality status:** For patients not hospitalized during the course of the study, a phone contact will be done 3 months after the last study drug intake to collect their mortality status.

¹³ **V1:** Visit 1 can be splitted into 2 separated visits for outpatients to follow site organization and quarantines requirement. However, the interval between these 2 visits cannot exceed 48 hours to ensure patients start the study treatment at an early stage of the disease. Date of first intake of study drug will be considered as D0.

5.2. Study conduct

It is the Investigator's responsibility to ensure that all the assessments are carried out during each visit and that the intervals between visits/follow-ups are adhered to.

5.2.1. Visit 1 – Day 0 (D0 / Baseline)

Patient with a PCR or Rapid Antigen tests diagnosis of COVID-19 will be informed about the general aspects of the study and will sign and date the informed consent form. Only when patient written informed consent has been collected may further study procedures be carried out.

The patient number will be allocated once the patient is created in the eCRF.

At baseline, the following assessments will be performed:

- All inclusion/exclusion criteria will be verified,
- Collection of the signed informed consent form,
- Demographic data collection: year of birth, gender and ethnicity,
- Medical history documentation including comorbidities or associated risks,
- Start date (Onset) of COVID-19 symptoms and contamination date if known,
- All current medications must be recorded and all changes must be documented during the course of the study,
- Complete physical examination,
- Vital signs, body weight and height measurement,
- Record a 12 leads ECG,
- Report the disease severity rating using the 7-point ordinal scale (i.e. Not hospitalized, no limitations on activities; Not hospitalized, limitation on activities; Hospitalized, not requiring supplemental oxygen; Hospitalized, requiring supplemental oxygen; Hospitalized, on non-invasive ventilation or high flow oxygen devices; Hospitalized, on invasive mechanical ventilation or ECMO; Death);
- Supply outpatients with oximeter, and explain purpose and how to use it
- Collect samples for
 - Analysis performed by local lab: Hematology, biochemistry, serum pregnancy test for women of child-bearing potential (- an additional urine pregnancy test can be done if the result of the serum test is not available at the time of the study drug dispensation)
 - Biobanking purposes:
 - Viral load testing (nasopharyngeal and blood),
 - CRP, Troponin I & T and D-dimer,
 - Cytokines testing,

- Immunophenotyping and cells activation markers (samples will be taken in selected sites and for approximately 100 patients)
- Hemostasis function exploration
- miRNA124 assessment (Blood PAXgene® tubes),
- Patient randomization,
- Dispensation of study treatment allocated to the patient once all the selection criteria have been confirmed (including laboratory assessments for patients' eligibility)
- Administration of the first intake on site for safety purpose; Instruct the patient how to take the study drug once at home.
- Record all adverse event (if any) starting from the informed consent signature,
- Schedule next on-site visit and/or remote medical monitoring.

Since COVID-19 positive patients are invited to take part to the study and considering sites potential organization and the quarantines requirements in participating countries, randomization visit can be splitted into 2 separated visits. However, the interval between these 2 visits cannot exceed 48 hours to ensure patients start the study treatment at an early stage of the disease.

Performing the visits at the patient's home is allowed as long as authorized as per local requirements and adequately organized with the site staff to ensure patients safety (i.e. visit to be performed by a physician and/or a nurse depending on the examinations left to be done at the patient's home, and both trained to the study protocol).

Besides, for patients not diagnosed yet but with a high suspicion of COVID-19 (i.e. showing symptoms and who went in contact with infected people) and with at last one risk factor, the PCR or Rapid Antigen tests can be performed as part as the study visit. Nevertheless, the randomization procedure must not be done until the COVID positive status of the patients is confirmed.

5.2.2. Follow-up of out-patients between D0 and D14

After D0, outpatients will be contacted every other day by the investigator or his/her designee.

During this remote medical monitoring, outpatients will be questioned on their state of health, including body temperature, SPO2, clinical signs and occurrence of any potential adverse events as well as any change in the current medication will be checked. Data will be recorded in the patient's medical chart and in the dedicated page of the eCRF.

In case of any sign of worsening, outpatients will be asked to come back to the study site for an unscheduled visit where additional examinations will be performed.

During the last daily contact, the D14 onsite visit will be confirmed to the patient. Patients will be asked to bring back the oximeter provided at D0.

If no quarantine period is applied or if patient migration to the study site is acceptable as per local country regulation, outpatients will perform a D7 visit on-site where the same examinations as hospitalized patients will be done.

In case of quarantine policy, sites should organize home care settings to collect samples at D7 at patients' home.

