5.2.3. Visit 2 – Day 7 (+/- 2 days)

For Patients hospitalized at D7 (or since D7), the following assessments will be performed:

- Change in current medication will be checked and recorded,
- Complete physical examination and only changes from last visit will be recorded,
- Vital signs measurement,
- Record a 12-leads ECG,
- Report the disease severity rating using the 7-point ordinal scale (i.e. Not hospitalized, no limitations on activities; Not hospitalized, limitation on activities; Hospitalized, not requiring supplemental oxygen; Hospitalized, requiring supplemental oxygen; Hospitalized, on non-invasive ventilation or high flow oxygen devices; Hospitalized, on invasive mechanical ventilation or ECMO; Death);
- Collect samples for
 - Analysis performed by local lab: Hematology, biochemistry

- Biobanking purposes:
 - Viral load testing (nasopharyngeal and blood),
 - CRP, Troponin I & T and D-dimer,
 - Hemostasis function exploration
- miRNA124 assessment (Blood PAXgene® tubes),
- Adverse Event and follow-up and reporting (if any).

NB: At any visit, for hospitalized patients: collect chest CT scan at discharge (\pm 7 days) and send to central reader for analysis. In addition, an evaluation of dyspnea severity will be done at discharge using the Medical Research Council (MRC) dyspnea scale.

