9.3.3. Analysis of Secondary Efficacy Endpoints

The following secondary endpoints will be analyzed. The analysis will be done on FAS population

- Rate of patients hospitalized
- Percentage of patients reporting each severity rating on a 7-point ordinal scale at each study visit (i.e. Not hospitalized, no limitations on activities; Not hospitalized, limitation on activities; Hospitalized, not requiring supplemental oxygen; Hospitalized, requiring supplemental oxygen; Hospitalized, on non-invasive ventilation or high flow oxygen devices; Hospitalized, on invasive mechanical ventilation or ECMO; Death)
- Change in the ranking on an ordinal scale from baseline to days 7, 14, 21, 28, 48 and at 3 months after the last study drug intake
- % change and AUC over time of oxygen saturation measured by daily pulse oximetry before hospitalization
- Rate of patients with SpO₂ ≤94% and rate of patients with SpO₂ ≤92% at Day 28
- Change from enrolment in inflammatory markers in plasma (i.e. MCP-1, MIP-1 α, G-CSF, IL-1b, IL-2, IL-6, IL-7, IL-10, IL-17, INF γ and TNF α) and in immune phenotype and assessment of cell-activation markers in PBMCs at D14, D28 for hospitalized patients only
- Rate of patients requiring oxygen supplementation
- Time to hospitalization (log rank) from baseline
- Time to assisted ventilation and oxygen supplementation (log rank) from baseline
- Number of days of assisted ventilation
- Number of days of oxygen supplementation
- Number of days at the hospital from admission to discharge ps
- Change from baseline in microRNA-124 levels in total blood (PAXgene®) at D0, D7 and
- AUC and % of change from enrolment in CRP, Troponin I & T and D-dimer levels
- Time to death and mortality rate (all causes, and Covid-19 related)
- Time to improvement of one level in the 7-point ordinal scale
- SARS-CoV-2 virus in nasopharyngeal sample and/or in blood at Day 0, 7 (hospitalized patients), 14, 21, and 28
- Change in SpO₂ values from D0 to D14 in the outpatient's population

In addition, exploratory analysis to assess the radiological findings for patients hospitalized because of Covid-19 infection consequences will be performed.

Central blinded review of the hospitalization discharge CT-Scans for descriptive analysis with regards to the disease severity and outcomes.

Additional details will be elaborated in the Statistical Analysis Plan (SAP).

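### Outpatients who cannot attend on site at D7 are assigned no 7-point score between D0 and the D14 visit, although two secondary endpoints use it

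*Protocol*

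**What the plan says.** Protocol 5.2.2 sets the frequency of contact: "After D0, outpatients will be contacted every other day by the investigator or his/her designee". At each contact, "outpatients will be questioned on their state of health, including body temperature, SPO2, clinical signs and occurrence of any potential adverse events"; changes in medication are also checked. Answers go on a dedicated eCRF page. The 7-point scale is not listed.

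The flow chart in 5.1 agrees. Its remote item is "Remote monitoring of body temperature, SPO2 and Clinical Signs of COVID-19", and the 7-point row is blank in the remote column. The D7 column is labelled "D7 for hosp. Patients/and potentially outpatients". Section 5.2.3, which contains the D7 rating, opens with "For Patients hospitalized at D7 (or since D7), the following assessments will be performed".

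Outpatients are not left out of D7 altogether. Section 3.1 says "Every attempt to perform the Day 7 on-site visit should be made anyway", and an outpatient who attends has the same examinations as an inpatient, so also the scale. For those in quarantine, 5.2.2 says "In case of quarantine policy, sites should organize home care settings to collect samples at D7 at patients' home". It mentions samples only.

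Section 9.3.3 lists two secondary endpoints that use the scale: change in rank from baseline to several days including day 7, and "Time to improvement of one level in the 7-point ordinal scale".

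**The concern.** Exclusion criterion 1 rules out patients who need oxygen, so an outpatient starts in one of the two non-hospitalised categories. The only improvement open to that patient is from limited to unlimited activities. One question on a call that is already being made would capture it. As written, the question is first due at D14 for anyone who cannot come to the site at D7.

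There are two consequences:

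- The day-7 endpoint has no value for these patients. Whether a value is missing depends on quarantine status and local rules, so the D7 distribution leans towards hospitalised patients and outpatients free to travel.
- Improvements on, say, day 4 and day 11 receive the same date. If many outpatients recover in the first two weeks, time to improvement loses much of its resolution.

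**Working it through.** **Which contacts carry the scale (outpatient, D0 to D14)**

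| Contact | Source | Scale assigned? |
|---|---|---|
| D0 visit | 5.2.1 | yes |
| Calls every 2 days | 5.2.2, flow chart | no |
| D7 on site, if it takes place | 3.1, 5.2.2, 5.2.3 | yes |
| D7 at home under quarantine | 5.2.2 | no, samples only |
| Unscheduled visit | 5.2.8 | yes in the text, blank in the flow chart; called for worsening |
| D14 visit, ±2 days | 5.2.4 | yes, so from D12 |

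Without an on-site D7 visit or an unscheduled visit, the first post-baseline score comes at D12 to D16.

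**The plan's own power figure.** Section 9.5 gives 78% for the primary endpoint. With unpooled variance, θ = 0.09 / √(0.84×0.16/533 + 0.75×0.25/267) = 2.913. The futility bound is Z1 ≤ √0.375 × (1.960 − 1.282×√0.625) = 0.580. If the stop is followed, power is 77.7%, so the figure reproduces. It does not use the 7-point scale and is unaffected here. No power is stated for time to improvement, so the rest is illustration.

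**Method for time to improvement.** This is the expected-count power of a grouped log-rank test, 2:1, one-sided 0.025. At each visit with r1, r0 at risk (r in total) and e1, e0 expected improvements (d in total):

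- U = Σ(e1 − d·r1/r)
- V = Σ d(r1/r)(r0/r)(r − d)/(r − 1)
- power = Φ(U/√V − 1.960)

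Assumptions not in the documents: exponential times, hazard ratio for improvement 1.2 to 1.3, control median 4 to 21 days, 400 or 800 patients all able to improve and all without D7, no dropout.

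**Worked case: N = 800, hazard ratio 1.25, control median 7 days.** By D14 the expected improvements are 439.1 of 533.3 and 200.0 of 266.7.

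- No D7 (visits D14, 21, 28, 48): U = 13.02 + 3.11 + 1.44 + 0.45 = 18.02; V = 28.61 + 9.74 + 4.56 + 0.85 = 43.76; U/√V = 2.72; power 77.7%.
- With D7: D7 contributes 14.14 to U and 44.00 to V, and D14 contributes 6.65 and 20.75. The later visits are unchanged. U = 25.79, V = 79.90, U/√V = 2.885; power 82.3%.
- Loss without D7: 4.6 points.

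**All medians.** The three power columns are for N = 800 and hazard ratio 1.25. The last column is the range over N = 400 or 800 and hazard ratios 1.2 to 1.3.

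| Control median | No D7 | With D7 | Every 2 days | Loss without D7, points |
|---|---|---|---|---|
| 4 days | 62.8% | 79.7% | 83.3% | 10 to 17 |
| 5 days | 71.0% | 81.3% | 83.1% | 7 to 11 |
| 7 days | 77.7% | 82.3% | 82.6% | 3 to 5 |
| 10 days | 80.3% | 82.0% | 81.7% | 1 to 2 |
| 14 days | 79.8% | 80.4% | 80.0% | under 1 |
| 21 days | 76.0% | 76.1% | 75.8% | about 0 |

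If only half the patients lack D7 (N = 800, hazard ratio 1.25), power is 70.5%, 75.4%, 79.4% and 79.9% at medians of 4, 5, 7 and 14 days. The losses are 9.2, 5.9, 2.9 and 0.5 points.

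**Second check.** A log-rank simulation used 480 outpatients (an assumed 60% of 800) and Weibull times. Power with no D7, with D7 and with ratings every 2 days was:

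- medians 6 versus 7 days, shape 1.5: 54%, 62%, 64%
- medians 6.8 versus 8 days, shape 1.5: 62%, 66%, 67%
- medians 6 versus 7 days, shape 1.2: 41%, 45%, 46%

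A D7 score is worth about 4 to 8 points here. Rating at every call adds 1 to 2 points more, with Monte Carlo error of about 0.9 points per estimate at 3,000 trials.

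**The case against.** The protocol does make provision for outpatients at D7. The on-site visit must be attempted and carries the scale, a quarantined patient should already have a home contact that day, and 5.2.1 allows home visits by trained staff, although it says so under Visit 1. This stands: the score is unassigned for patients kept at home, not ruled out, and the number affected is unknown.

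A reader might infer that such a patient cannot be seen to improve before D14. The D14 window opens at D12, and 5.2.8 includes the scale at unscheduled visits, so that is slightly too strong.

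A reader might also infer a definite power loss. The documents do not support one. Section 9.3.3 specifies log-rank for other endpoints but not for time to improvement, 9.3.1 offers only Kaplan-Meier plots for time-to-event variables, and no effect size is given. Patients with no activity limitation at D0 cannot improve under any schedule, which lowers the effective sample size below the figures used above. The direction is robust, since losing D7 never raised power in any case run. The size is not.

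Finally, SAP 4.13 removes this endpoint along with all other efficacy analyses after the futility stop. That limits the point to the design of the protocol.

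**Conclusion.** The gap holds as a minor design point. Followed as written, the schedule gives an outpatient without an on-site D7 visit no score from D0 until about D12 to D14, unless an unscheduled visit occurs. The missing day-7 value follows from the text and needs no assumption.

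The power cost for time to improvement does need assumptions. It is near 0 for slow recovery and roughly 3 to 17 points for medians of about 4 to 8 days. The upper end requires a 4-day median and every patient missing D7.

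It would be wrong to read this as a biased comparison. The schedule is the same in both blinded arms, so coarser dating does not by itself favour either arm under the null hypothesis. The primary endpoint and its 78% power do not change.

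**What to change.** When there is no on-site D7 visit, record the 7-point scale at the D7 home sampling contact or at the D6 or D8 call, and use it as the D7 score. Both calls fall within D7 ±2 days. With Visit 1 counted as Day 1, they are SAP days 7 and 9, inside the Visit 2 window of days 2 to 10. Add the item to the remote-contact eCRF page and to the flow chart, and align the flow chart's unscheduled column with 5.2.8.

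Rating at every 2-day call is optional. In the cases run it added at most about 4 points beyond the D7 score, and nothing when recovery was slow.

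The cost is one question on an existing contact and one eCRF field. The drawback is that ratings by phone are slightly less standardised than ratings on site.
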